## List of Abbreviations

| Abbreviation   | Definition                                                                                                                          |
|----------------|-------------------------------------------------------------------------------------------------------------------------------------|
| ADL            | activities of daily living                                                                                                          |
| AE             | adverse event                                                                                                                       |
| ALT            | alanine transaminase                                                                                                                |
| AST            | aspartate transaminase                                                                                                              |
| BMI            | body mass index                                                                                                                     |
| CF             | cystic fibrosis                                                                                                                     |
| CFTR    | cystic fibrosis transmembrane conductance regulator gene                                                                            |
| CFTR           | cystic fibrosis transmembrane conductance regulator protein                                                                         |
| CRF            | case report form                                                                                                                    |
| CSR            | clinical study report                                                                                                               |
| CTCAE          | Common Terminology Criteria for Adverse Events                                                                                      |
| CYP            | cytochrome P450                                                                                                                     |
| ECG            | electrocardiogram                                                                                                                   |
| EDC            | electronic data capture                                                                                                             |
| EENT           | eyes, ears, nose, and throat                                                                                                        |
| ELX            | ellexacaftor                                                                                                                        |
| ETT            | Early Termination of Treatment                                                                                                      |
| EU             | European Union                                                                                                                      |
| F508del | CFTR gene mutation with an in-frame deletion of a phenylalanine codon corresponding to position 508 of the wild-type protein |
| FDA            | Food and Drug Administration                                                                                                        |
| FDC            | fixed-dose combination                                                                                                              |
| FSH            | follicle-stimulating hormone                                                                                                        |
| GCP            | Good Clinical Practice                                                                                                              |
| GPS            | Global Patient Safety                                                                                                               |
| HIPAA          | Health Insurance Portability and Accountability Act                                                                                 |
| HR             | heart rate                                                                                                                          |
| ICF            | informed consent form                                                                                                               |
| ICH            | International Council for Harmonization                                                                                             |
| IEC            | independent ethics committee                                                                                                        |
| IMP            | investigational medicinal product                                                                                                   |
| IND            | Investigational New Drug (application) (US)                                                                                         |
| IPD            | important protocol deviation                                                                                                        |
| IRB            | institutional review board                                                                                                          |
| IVA            | ivacaftor                                                                                                                           |
| LUM            | lumacaftor                                                                                                                          |
| max            | maximum value                                                                                                                       |
| min            | minimum value                                                                                                                       |
| n              | size of subsample                                                                                                                   |
| OATP1B1        | organic anion transporter protein 1B1                                                                                               |
| PE             | physical examination                                                                                                                |
| P-gp           | P-glycoprotein                                                                                                                      |

| Abbreviation | Definition                                                                                        |
|---------------------|----------------------------------------------------------------------------------------------------------|
| PI                  | principal investigator                                                                                   |
| ppFEV 1  | percent predicted forced expiratory volume in 1 second                                                   |
| PR                  | PR interval, segment                                                                                     |
| PT                  | Preferred Term                                                                                           |
| QRS                 | the portion of an ECG comprising the Q, R, and S waves, together representing ventricular depolarization |
| QT                  | QT interval                                                                                              |
| QTcF                | QT interval corrected by Fridericia's formula                                                            |
| RR                  | interval from the onset of 1 QRS complex to the next                                                     |
| SAE                 | serious adverse event                                                                                    |
| SAP                 | statistical analysis plan                                                                                |
| SD                  | standard deviation                                                                                       |
| SI                  | SI units (International System of Units)                                                                 |
| SOC                 | System Organ Class                                                                                       |
| SUSAR               | suspected, unexpected, serious adverse reaction                                                          |
| TE                  | treatment-emergent                                                                                       |
| TEAE                | treatment-emergent adverse event                                                                         |
| TEZ                 | tezacaftor                                                                                               |
| ULN                 | upper limit of normal                                                                                    |
| US                  | United States                                                                                            |
| USA                 | United States of America                                                                                 |

## 5 INTRODUCTION

### 5.1 Background

Cystic fibrosis (CF) is an autosomal recessive genetic disease with serious morbidities and frequent premature mortality. CF affects more than 80,000 individuals worldwide (approximately 31,000 in the US and 49,000 in the EU).

CF is caused by decreased quantity and/or function of the CFTR protein due to mutations in the *CFTR* gene. CFTR is a channel that regulates the flow of chloride and other anions across epithelia in multiple organs and tissues, including the lungs, pancreas and other gastrointestinal organs, and sweat glands. Despite progress in the treatment of CF with symptomatic therapies, the current median age at death among people with CF is approximately 30 years, and the predicted median age of survival is approximately 47 years. More effective treatments are needed for CF.

The most common disease-causing mutation is *F508del*: approximately 85.3% of people with CF in the US and 80.6% in Europe have at least one *F508del* allele.

At present CF does not have a cure. CFTR modulators (i.e., correctors and potentiators) represent a major advancement in the treatment of CF because they are systemic therapies that target the underlying cause of the disease and have been shown to improve CF survival by modifying the course of disease. The clinical testing and regulatory approval of CFTR modulators in certain countries for the treatment of people with CF caused by specific *CFTR* genotypes have established the therapeutic value of specific regimens developed by Vertex. These treatment regimens include ivacaftor (IVA) monotherapy (KalydecoTM), lumacaftor (LUM)/IVA dual combination therapy (OrkambiTM), tezacaftor (TEZ)/IVA dual combination therapy (SymdekoTM, SymkeviTM) and elexacaftor (ELX)/TEZ/IVA triple combination therapy (TrikaftaTM, KaftrioTM).

The ELX/TEZ/IVA regimen is the first medicine to demonstrate clinical benefit in patients with a single *F508del* allele, regardless of the mutation of the second allele. A pivotal Phase 3 program in CF subjects 12 years of age or older demonstrated that ELX/TEZ/IVA provides substantial improvements in lung function, CFTR function, and nutritional status, and was generally safe and well tolerated with a low rate of treatment discontinuation.

### 5.2 Study Rationale

This study will evaluate the safety of 48 weeks of treatment with ELX/TEZ/IVA in subjects with CF who complete a parent study (VX19-445-117 or VX20-445-126). The potential for benefit in these patients is supported by published Phase 2 and publicly disclosed Phase 3 clinical data in subjects with CF. In addition, ELX/TEZ/IVA is generally safe and well tolerated (refer to ELX/TEZ/IVA Investigator's Brochure).

Data from this study are intended to enrich the body of evidence showing that ELX/TEZ/IVA is safe and well tolerated in subjects with CF.

## 6 STUDY OBJECTIVES

### 6.1 Primary Objective

To evaluate the safety and tolerability of ELX/TEZ/IVA in subjects with CF

## 7 STUDY ENDPOINTS

### 7.1 Primary Endpoint

Safety and tolerability of ELX/TEZ/IVA based on adverse events (AEs), clinical laboratory values, ECGs, vital signs, and pulse oximetry

## 8 STUDY POPULATION

Eligibility will be reviewed and documented by an appropriately qualified member of the investigator's team before subjects are enrolled.

Subjects who meet all of the inclusion criteria and none of the exclusion criteria will be eligible. In the criteria below, "parent study" is defined as VX19-445-117 or VX20-445-126.

### 8.1 Inclusion Criteria

1. Subject (or his or her legally appointed and authorized representative) will sign and date an informed consent form (ICF) and, when appropriate, an assent form.
2. Willing and able to comply with scheduled visits, treatment plan, study restrictions, laboratory tests, contraceptive guidelines, and other study procedures.
3. Did not withdraw consent from a parent study.
4. Meets at least 1 of the following criteria:
  - Completed study drug treatment in a parent study.
  - Had study drug interruption(s) in a parent study, but did not permanently discontinue study drug, and completed study visits up to the last scheduled visit of the Treatment Period of a parent study.
5. For subjects being considered for resumption of participation in this study after enrolling in another Vertex study of investigational CFTR modulators (referred to as "another qualified Vertex study"): Completed the ETT visit in another qualified Vertex study before or on the same day as the Returning Visit in this study. If more than 30 days have elapsed since the ETT visit in the other qualified Vertex study, approval of the medical monitor is required.
6. Willing to remain on a stable CF treatment regimen (as defined in Section 9.5) through completion of study participation.

### 8.2 Exclusion Criteria

1. History of any comorbidity that, in the opinion of the investigator, might confound the results of the study or pose an additional risk in administering study drug to the subject.
2. History of drug intolerance in a parent study that would pose an additional risk to the subject in the opinion of the investigator (e.g., subjects with a history of allergy or hypersensitivity to the study drug).
3. Pregnant and breast-feeding females. Female subjects must have a negative pregnancy test at the Day 1 Visit before receiving the first dose of study drug.
4. Current participation in an investigational drug trial other than a parent study. Participation in a noninterventional study (including observational studies, registry studies, and studies

requiring blood collections without administration of study drug) and screening for another Vertex study is permitted.

5. For subjects being considered for resumption of participation in this study after enrolling in another qualified Vertex study, the following exclusion criteria also apply:

- Subject received the first dose of study drug in the Treatment Period of another qualified Vertex study,
- Subject has access to commercially available ELX/TEZ/IVA or is receiving managed-access-program-supplied ELX/TEZ/IVA, or
- Subject departed this study more than once to participate in another qualified Vertex study.

[figure not shown]
## 9 STUDY IMPLEMENTATION

### 9.1 Study Design

This is a Phase 3b, multicenter, open-label study for subjects who complete a parent study (VX19-445-117 or VX20-445-126) and meet eligibility criteria (Section 8). A schematic of the study design is shown in Figure 9-1.

Study visits and assessments are shown in Table 3-1. All visits will occur within the windows specified.

**Figure 9-1 VX20-445-121 Study Design**

ELX: elexacaftor; IVA: ivacaftor; TEZ: tezacaftor

Note: Figure is not drawn to scale.

Subjects will receive a dose of ELX 200 mg once daily (qd)/TEZ 100 mg qd/IVA 150 mg every 12 hours (q12h).

For treatment continuity in regions where ELX/TEZ/IVA is not commercially available, an option to return to this study will be offered to subjects who depart this study to enroll in another qualified Vertex study based on the following:

- Subjects have received open-label ELX/TEZ/IVA during the other study's Run-in Period but have not received study drug in the Treatment Period of the other study, and
- Meet all eligibility criteria for this study (Section 8) at their Returning Visit.

Subjects who resume participation in this study will resume treatment with study drug after completion of a Returning Visit. Resumption of participation in this study following departure to another qualified Vertex study will be permitted only once.

### **9.1.1 Treatment Period**

Treatment Period assessments are listed in Table 3-1.

Subjects will receive the first dose of study drug on Day 1 after obtaining informed consent (and assent, when applicable) and confirming eligibility. Subjects who enroll in this study on a study drug interruption from a parent study or another qualified Vertex study will NOT receive the first dose of study drug until they meet the resumption criteria in Section 9.8; before receiving study drug, subjects will repeat all Day 1 assessments.

Study drug administration details are provided in Section 9.6.

The Day 1 Visit should be on the same day as the last scheduled visit of a parent study. Subjects whose Day 1 Visit is NOT within 1 day of the last scheduled visit of a parent study will repeat all Day 1 assessments.

Subjects whose Day 1 Visit is within 1 day of the last scheduled visit of a parent study will NOT have to repeat any Day 1 assessments that were specified to be performed at the last scheduled visit in a parent study.

### **Subjects Resuming Participation After Discontinuation From Another Qualified Vertex Study**

Subjects who resume participation in this study will complete the Returning Visit and resume treatment with ELX/TEZ/IVA after completion of the Returning Visit. Study visit numbering for returning subjects will resume based on the last study visit before the Departing Visit in this study.

The Early Termination of Treatment (ETT) Visit in another qualified Vertex study and the Returning Visit in this study may occur on the same day. If completed on the same day or within 1 calendar day, any assessments completed at the ETT in the other qualified Vertex study do not have to be repeated at the Returning Visit in this study.

Subjects who resume participation but have their first dose of study drug in this study delayed will repeat the safety assessments specified to be performed at the Returning Visit before receiving their first dose of study drug (see Section 3).

If the subject's Returning Visit window coincides with a scheduled study visit in this study, only the Returning Visit assessments will be completed, after which subjects will resume study visits in this study.

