#### **11.2.2 Clinical Laboratory Assessments**

Blood and urine samples will be analyzed at a central laboratory, with the exception of the urine pregnancy test. As described below, urine pregnancy tests will either be analyzed by the site or at home using a home pregnancy test kit. On Day 1 (and the Returning Visit if applicable), blood samples will be collected before the first dose of the study drug.

Laboratory test results that are abnormal and considered clinically significant will be reported as AEs (see Section 13.1).

The safety laboratory test panels are shown in Table 11-1.

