## 7.2 Sample Size and Power

The primary objective of the study is the evaluation of the safety of ELX/TEZ/IVA. This is an open-label extension study that will enroll the subjects from parent studies who meet eligibility criteria in this study.

Up to approximately 160 subjects are expected to enroll in this open-label extension study.

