## **9.3           Safety Analysis**

The primary objective of this study is the evaluation of safety and tolerability of ELX/TEZ/IVA. All safety analyses will be based on the TE Period for subjects in the Safety Set.

The overall long-term safety profile of study drug will be assessed in terms of the following safety and tolerability endpoints:

- Treatment-emergent adverse events (TEAEs)
- Clinical laboratory values
- ECGs
- Vital signs
- Pulse oximetry

Only descriptive analysis of safety will be performed and no statistical testing will be performed.

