### **9.3.1        Adverse Events**

AEs will be classified as pretreatment AEs, TEAEs, or post-treatment AEs, defined as follows:

- **Pre-treatment AE:** any AE occurred before the first dose date of study drug in the TE Period. For subjects who were enrolled in another qualified Vertex study before completing this study and resume participation in this study, AEs that started during participation in another qualified Vertex study and were ongoing at the time of Returning Visit will be flagged as pre-treatment AE.
- **TEAE:** any AE that worsened (either in severity or seriousness) or newly developed at or after the first dose date of ELX/TEZ/IVA in the TE Period in this open-label study.
- **Post-treatment AE:** any AE that worsened (either in severity or seriousness) or newly developed after the TE Period.

For AEs with missing or partial start dates, if there is no clear evidence that the AEs started before or after study drug treatment start date in this OLS, then the AEs will be classified as TEAEs.

Details for imputing missing or partial start dates of adverse events are described in [Appendix C](#).

An overview of all TEAEs during TE period will be summarized and include the following categories:

- Number of TEAEs (total number of TEAEs only)
- Subjects with any TEAEs
- Subjects with TEAEs by strongest relationship
- Subjects with TEAEs by maximum severity
- Subjects with TEAEs leading to study drug discontinuation
- Subjects with TEAEs leading to study drug interruption
- Subjects with Grade 3/4/5 TEAEs
- Subjects with related TEAEs
- Subjects with serious TEAEs
- Subjects with related serious TEAEs
- Subjects with TEAE leading to death

The frequency counts and percentages will be presented for the above overview table.

The following summary tables of TEAEs will be presented for overall:

- All TEAEs
- Grade 3/4/5 TEAEs
- TEAEs by strongest relationship
- TEAEs by maximum severity
- TEAEs leading to treatment discontinuation
- TEAEs leading to treatment interruption
- Related TEAEs
- Serious TEAEs
- Related serious TEAEs
- TEAEs leading to death

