## 12 APPENDICES

### Appendix A: Analysis Visit Windows for Safety Assessments

Table 12-1 Analysis Visit Windows Safety Assessments			
Assessment	Visit	Target Study Day	Analysis Visit Window (in study days)
Weight, Height and BMI	Baseline	--	defined in section 9.1
	OL Week 12	85	[1, 127] where Day 1 is post-dose measurement
	OL Week 24	169	(127, 211]
	OL Week 36	253	(211, 295]
	OL Week 48	337	(295, 351]
	OL Safety Follow-up	Not applicable	Use nominal visit
Vital Signs Hematology Serum Chemistry	Baseline	--	defined in section 9.1
	OL Week 12	85	[1, 127] where Day 1 is post-dose measurement
	OL Week 24	169	(127, 211]
	OL Week 36	253	(211, 295]
	OL Week 48	337	(295, 351]
	OL Safety Follow-up	Not applicable	Use nominal visit
Standard 12-lead ECG	Baseline	--	defined in section 9.1
	OL ETT or Departing	Not applicable	Use nominal visit (ETT or Departing Visit)
	OL Safety Follow-up	Not applicable	Use nominal visit
Coagulation 	Baseline	--	defined in section 9.1
	OL Week 24	169	[1, 253] where Day 1 is post-dose measurement
	OL Week 48	337	(253, 351]
	OL Safety Follow-up	Not applicable	Use nominal visit

Notes:

 Visit name for analysis purpose is used to report data in tables and figures.

 The analysis visit windows will be applied using the following rules for both scheduled and unscheduled visits:

1. If no numerical measurement is available within a visit window, the measurement will be considered missing for the visit.
2. If there is more than 1 numerical measurement available within a visit window, use the following rules:
  - i. The measurement closest to the target day will be used; or
  - ii. If there are multiple measurements with the same distance from the target day, the latest measurement will be used. If the latest measurement cannot be determined, then unscheduled visit will be selected.

 For measurement collected on the date of first dose of study drug in Treatment Period, if it cannot be determined whether the measurement is before or after the first dose:

1. Scheduled measurement will be treated as pre-dose observation.
2. Unscheduled measurement will be treated as post-dose observation.

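### For subjects who leave and return, the SAP counts values taken before treatment resumes as treatment-emergent, because it omits the protocol's exclusion and screens pre-dose values only at the original first dose

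*Protocol*

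**What the plan says.** **Protocol**
- 9.1.1 (returning subjects) and Table 3-1, footnote d: "If the subject's Returning Visit window coincides with a scheduled study visit in this study, only the Returning Visit assessments will be completed". Study drug restarts after the Returning Visit. If the first dose is delayed, the safety assessments are repeated before it.
- 11.2.2: "On Day 1 (and the Returning Visit if applicable), blood samples will be collected before the first dose of the study drug".
- 8.1, criterion 5, on the gap before return: "If more than 30 days have elapsed since the ETT visit in the other qualified Vertex study, approval of the medical monitor is required".
- 9.1: returners have taken open-label ELX/TEZ/IVA in the other study's Run-in Period and no study drug of its Treatment Period.
- 12.3.1: for returners, time in the other study is left out of the TE Period.

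**SAP**
- 9.1: the TE Period runs from first dose to 28 days after last dose, or to completion of participation if earlier. It has no exclusion for time away.
- Appendix A, Table 12-1, note 2: "The analysis visit windows will be applied using the following rules for both scheduled and unscheduled visits". The value closest to the target day is chosen. Pre-dose values are screened out only at the original first dose (the Day 1 entry in the table, and note 3).
- 9.3.2 to 9.3.4: threshold summaries use values in the TE Period. 9.3.5 does the same for the lowest oxygen saturation.
- 9.3.1: "AEs that started during participation in another qualified Vertex study and were ongoing at the time of Returning Visit will be flagged as pre-treatment AE".
- 9.2.4 to 9.2.6: prior medication, exposure and compliance each have a rule for returners.

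**The concern.** The SAP handles the absence for exposure, compliance, prior medication and AEs, but not for laboratory, vital-sign, weight, ECG or oximetry values. As written, a value taken after departure and before treatment resumes in this study counts as treatment-emergent and can stand as a by-visit result.

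The report can then contradict itself. Take an ALT elevation of 6 × ULN (an illustrative figure) that began in the other study and is still present at the Returning Visit. The AE table leaves it out as pre-treatment. The threshold table counts the same finding as a treatment-emergent event above 5 × ULN. These are the primary safety outputs of the study, and a reader could not tell which classification was meant.

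**Working it through.** **1. The SAP's own windows reproduce.** Target day = 7 × week + 1, which gives 85, 169, 253 and 337. Each limit is the midpoint of adjacent targets: (85 + 169)/2 = 127, (169 + 253)/2 = 211, (253 + 337)/2 = 295. The last limit is 337 + 14 = 351. For coagulation, (169 + 337)/2 = 253, then 351. All match Table 12-1. Days 1 to 351 are covered without a gap.

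**2. Where a Returning Visit value lands (weight, vital signs, hematology, chemistry).**
- Within ±5 days of Week 12, 24 or 36 (Days 80–90, 164–174, 248–258), it falls in that week's window, at most 5 days from target, and is normally the value chosen.
- At telephone Weeks 8 and 16 it enters the Week 12 window, at Weeks 20 and 28 the Week 24 window, and at Weeks 32 and 40 the Week 36 window. Each is 28 days from target, so it is used when nothing closer exists.

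Coincidence with a scheduled visit is therefore not needed. Any Returning Visit value on Days 1 to 351 is windowed.

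**3. Example (days assumed).** Depart Day 140, return Day 185. Both lie in the Week 24 window (127, 211]. Distances from target are |140 − 169| = 29 and |185 − 169| = 16, so the Returning Visit value is reported for Week 24. This holds under both visit clocks in the protocol. Counted from Day 1 (Section 3), the Week 24 visit fell during the absence. If numbering pauses while away (one reading of 9.1.1), the Week 24 visit moves to 169 + (185 − 140) = Day 214, outside the window.

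**4. Limits by visit and assessment.**
- *Week 48.* On the Day 1 clock, dosing ends the evening before Week 48. A return on Day 337 leaves no dosing, and an earlier return is normally outranked by the actual Week 48 visit. If numbering pauses while study days run on, an absence of a days puts the Week 48 visit at Day 337 + a. That is beyond Day 351 once a exceeds 351 − 337 = 14, and a Returning Visit value can then fill Week 48.
- *Coagulation.* Only Weeks 24 and 48 have windows.
- *ECG.* Table 12-1 has only baseline, ETT/Departing and Safety Follow-up, so by-visit tables are not affected. ECG threshold counts are.

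**5. Treatment of the same visit, side by side.**

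| Item | Rule for returners | Finding already present at the Returning Visit |
|---|---|---|
| AE begun in the other study and ongoing (SAP 9.3.1) | Yes | Pre-treatment |
| Exposure, compliance (SAP 9.2.5, 9.2.6) | Yes | Time in the other study left out |
| TE Period, protocol 12.3.1 | Yes | Time in the other study left out; Returning Visit and any gap before it not addressed |
| TE Period, SAP 9.1 | No | Inside the period |
| Threshold, maximum, minimum (SAP 9.1, 9.3.2–9.3.5) | No | Counted as treatment-emergent |

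**6. Size.** The SAP expects: "Up to approximately 160 subjects are expected to enroll in this open-label extension study". One event is 1/160 = 0.625%, about 0.6 percentage points. The number of returners is not given. If 1, 5, 10 or 20 subjects returned (an assumption), at most 0.6%, 3.1%, 6.3% or 12.5% of 160 could be touched.

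**The case against.** The strongest reply is that these values are on-drug anyway. Protocol Section 3 puts assessments before dosing at every visit, so an ordinary Week 24 value is pre-dose too. Returners took the same combination in the other study's Run-in, and that study's ETT visit may fall on the day of return. This stands. A reader might infer that Returning Visit values are off-drug or show a washed-out state; the documents do not support that in general. Such a value is off-drug only after a gap, an interruption or a delayed first dose. The protocol foresees all three (8.1 criterion 5; 9.1.1).

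It does not remove the inconsistency. The SAP screens out pre-dose Day 1 values by reference to the first dose in this study, although subjects arrive from parent studies of ELX/TEZ/IVA. It classifies AEs at return in the same way. Only the measured values lack a matching rule.

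Other points that stand:
- The coincidence sentence is not itself defective. The Returning Visit comprises all Day 1 assessments, so no Week 12, 24 or 36 measurement is lost.
- When the other study's ETT visit is within 1 calendar day, assessments need not be repeated, and there may be no Returning Visit value to window.
- The threshold problem is largely a mismatch between protocol and SAP. Restoring the exclusion alone would still leave open whether the Returning Visit, or a gap before it, counts as time in the other study.
- Removing the values from every table could hide a real signal, because the matching AE is already outside the TEAE tables.

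**Conclusion.** The point holds in limited form. The SAP lacks the protocol's TE exclusion and has no rule for values taken between departure and the first dose after return. They are windowed mainly as Week 12, 24 or 36 results and counted in TE threshold and maximum/minimum summaries, including ECG thresholds, at odds with the AE rule.

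A reader might infer that Week 48 and the ECG by-visit tables are equally affected. They are not: Week 48 is affected mainly if numbering pauses while study days run on, and the ECG by-visit tables are untouched. Nor can a share of returners with a misassigned value be calculated. The documents give no number of returners, departure days or lengths of absence, and selection of a Returning Visit value is not in itself an error.

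The effect is small. It is confined to subjects who return, which is allowed once, and it concerns summaries only: "Only descriptive analysis of safety will be performed and no statistical testing will be performed". The conclusion assumes that study day keeps running from the original first dose, since the SAP does not define it for returners.

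**What to change.** 1. **SAP 9.1.** Carry over the protocol's TE Period exclusion for returners, and state that it runs from departure to the first dose after return.
2. **SAP Appendix A.** Add a note that values taken after the Departing Visit and before the first dose after return, including any repeat before a delayed first dose, are pre-resumption values. They do not enter TE threshold, shift, maximum or minimum derivations, in line with the Day 1 rule and the AE rule. Show them flagged in a separate returner summary or listing, with time since the last ELX/TEZ/IVA dose, so that no signal is hidden.
3. **By-visit tables.** Where the window holds a value taken on treatment in this study, use it. Otherwise, show the Returning Visit value with a flag. Leaving that analysis visit blank is debatable, because the subject may have been on the same drug throughout.
4. **Study day.** Define it for returners, and say which visit clock the windows follow.

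Cost: a few SAP sentences and a date filter in programming, with no extra visits. The time-since-dose column needs the last ELX/TEZ/IVA dose date from the other study, which is also a Vertex study. The downside is that a few returners' values move out of the main TE summaries.
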